8.7 Specimen Collection

PrismRA arm:

Blood will be collected at Visits 1, 3, and 4. Blood will not be collected at Visit 2.

Blood will be collected in two 2.5 mL PAXgene tubes and one 8-10 mL serum separator tube for a total of 15 mL at Visit 1. Blood will be collected using the PrismRA sample collection kit at Visit 1 and processed according to the study sample collection process. Blood for the CRP test will be collected at Visits 1, 3, and 4 utilizing the same local lab and processed per standard lab practices.

Anticipated volume of blood to be drawn per patient over the scheduled study visits should not exceed 45 mL. If the initial blood draw in Visit 1 fails sample quality assessments, a patient may have an unscheduled study visit performed for an additional blood draw prior to Visit 2.

External control arm:

No specimen collection schedule is enforced, and the specimen collection is based on routine clinical encounters. OM1 does not handle specimens and utilizes the laboratory results only.

8.8 Study Treatment

PrismRA arm:

Patients are to initiate a b/tsDMARD or change to a study-indicated b/tsDMARD per clinical guidance of the Investigator on Visit 2.

External control arm:

b/tsDMARDs initiated by the treating physician according to the standard of care will be deemed as the study treatment. The study treatment can include the very first b/tsDMARD (new initiation) or subsequent b/tsDMARD (switch).

8.8.1 Randomization

No randomization will be performed for this study.

8.8.2 Stratification

There will be no stratification for this study.

8.8.3 Therapy, Dose, Modes of Administration

PrismRA arm:

- Dosage and selection of b/tsDMARD are at the Investigator's discretion but should be within the FDA approved label.
- Dose adjustments for a particular b/tsDMARD will be permitted only in accordance with the FDA approved label. Changes should be documented in the patient's medical records.

External control arm:

The selection and the initial dosage and dose adjustments are at the discretion of the treating physician and are assumed to be compatible with FDA approval.

8.8.4 Duration of Follow-up for Outcome Assessment

- 24 weeks from the index date, defined as the date of b/tsDMARDs initiation (See Section 8.5 for allowable time windows)

8.8.5 Medication Expenses and Reimbursement (PrismRA arm only)

- The Sponsor will not cover any b/tsDMARD medication costs associated with this study.
- Patients may be reimbursed for their time at the discretion of the Investigator.

8.9 Data Collection

PrismRA arm:

Patient data will be collected from clinical assessments, medical records, imaging, laboratory results, and surveys at screening/baseline, treatment initiation and follow-up visits and entered in the study database.

If a completed medical records release form is on file, comprehensive demographic, medical, and health information (if available) may be directly collected from the patient's electronic medical records by the Sponsor. Electronic Medical Records (EMR) data may be obtained indefinitely following a patient's enrollment unless the patient withdraws authorization.

Data from the PrismRA (Visit 1) samples will be stored at Scipher Medicine's Clinical Laboratory Improvement Amendments (CLIA)-certified and College of American Pathologists (CAP)-accredited laboratory.

External control arm:

In the external control arm, the existing data in OM1's PremiOM RA will be utilized. No new data collection will be performed.

8.10 Patient Follow-up

PrismRA arm:

In order to reduce the loss of patients to follow-up, all patients will be asked for their personal contact information and an alternate person's contact information. Patients may be directly contacted by the Investigator or Sponsor/designee in order to support study follow-up. The designated alternate contact person may also be directly contacted in the event the patient cannot be reached.

For patients who are lost to follow-up, Investigator or Sponsor/designee will search available health status databases to determine vital status and cause of death in case of mortality.

External control arm:

To ensure the availability of sufficient quality of data, at least one CDAI measurement during the baseline 3-month period prior to the index date (initiation of b/tsDMARDs) will be required. As needed, we will further require CDAI during the follow-up.

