6 Concomitant treatments including but not limited to the following are permitted per standard of care: 
 • csDMARDs (e.g., methotrexate, sulfasalazine, leflunomide, or hydroxychloroquine) • Non-steroidal anti-inflammatory drugs (NSAIDs) • Corticosteroids • Prednisone (or equivalent) at a stable \leq 10 mg per day for at least 2 weeks prior to Visit 1 • Intra-articular or parenteral corticosteroids \leq 2 weeks prior to Visit 1 	Concomitant treatments per standard of care will be allowed and recorded.
7 Patient is willing and able to complete the informed consent process and comply with study procedures and visit schedule.	This criterion is not replicable with real world dispensing data and will not be used.
8 This additional point does not apply to the PrismRA arm.	Patients will have \geq 1 CDAI measured in the 3-month period prior to the b/tsDMARD initiation to ensure patients from practices where CDAIs are routinely used and baseline CDAI is well defined in this 3-month window. There will be a further required \geq 3 CDAI measurements in the 12-month period prior to the b/tsDMARD initiation. If possible to retain enough patients to fully match the PrismRA arm, there will be a

	
required ≥ 4 CDAI measurements in the 12-month period prior to the b/tsDMARD initiation.
 
To ensure sufficient medical history information and past b/tsDMARDs usage history, at least 12 months of enrollment in the database prior to the study treatment initiation will be required. All history information prior to 12 months will also be utilized.

--	---

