10.5 Missing Data Handling

Missing data will be handled with two approaches: (1) minimizing the chance of missing data in the study design and conduct stages, and (2) handling missing data with statistical methods in the analysis phase.

The following measures will be taken to reduce missing data in the analysis datasets.

PrismRA arm:

Missing data will be minimized through rigorous conduct of data collection as described in Section 8.9. See below for the handling of missing follow-up data.

External control arm:

At least one observed CDAI in the 3-month period prior to the index date (b/tsDMARD initiation) will be required to ensure patients are selected from practices where CDAI are recorded as a part of routine care.

The following statistical methods will be considered in handling missing data in the analyses.

- For outcome measures, the appropriate methods depend on the magnitude of missing data, and whether data are assumed to be missing at random. This will be evaluated prior to the final analysis and will be evaluated for the PrismRA arm and the external control arm separately. Considerations will be given to multiple imputation, estimating the CDAI outcome (whether MID was achieved at Week 24) based on previous outcome measures and treatment status, and complete case analyses. A sensitivity analysis will be conducted to assess the robustness of the analysis results. Details will be provided in the SAP.

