5.4 Handling Missing Data

Missing data will be handled with two approaches: (1) minimizing the chance of missing data in the study design and conduct stages, and (2) handling missing data with statistical methods in the analysis phase.

The following measures will be taken to reduce missing data in the study design.

PrismRA arm: Missing data will be minimized through rigorous conduct of data collection as described in Section 8.9 of the Protocol. See below for the handling of missing follow-up data.

External control arm: At least one observed CDAI measurement in the 3-month period prior to the index date (b/tsDMARD initiation) and at least three observed CDAI measurements in the 12-month period prior to the index date (including the measurements in the aforementioned 3-month period) will be required to ensure patients are selected from practices where CDAI are recorded as a part of routine care.

The following statistical methods will be considered in handling missing data in the analyses.

The rigorous design of the study aims to reduce the amount of missing data in baseline variables. If needed, single imputation [8] of missing baseline characteristics will be used to ensure that all eligible patients are included in the PS model to estimate the probability of treatment [9] for confounding control. Further details of the treatment PS methods are described below in Section 6.3.

Longitudinal outcomes may be unobserved due to patients that are lost-to-follow up ("drop-out"), missed scheduled visits (PrismRA arm), encounters that fall outside of the specified follow up window (external control arm) or not measured during a completed visit. It is anticipated that at 24-weeks roughly 45% of the PrismRA arm and 50% of the external control arm will be missing outcome data. Within each study arm the number and proportion of missing outcomes at

12 and 24-week visits will be described and baseline characteristics of patients with complete versus incomplete outcome data will be compared.

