For the primary efficacy analysis multiple imputation (MI) will be used with the assumption that patients with unreported outcome measures at 12 and 24 weeks have outcome events that are non-informative under the missing at random (MAR) assumption. This assumes that missingness occurs independent of the unobserved outcome: that is, the possibly unknown true outcome for a patient is the same regardless of whether it is actually observed. This assumption underlies the ITT principle, which analyses all eligible patients according to the treatment group to which they were assigned regardless of subsequent missingness.

For all approaches using MI, fully conditional specification (FCS) methods will be used, which assume the existence of a joint distribution for all variables. [10] All eligible patients meeting inclusion and exclusion criteria and initiating the study treatment will be used to impute missing observations. Imputation models will include all relevant available observations at baseline and 12 and 24 week follow up visits. Separate MI models will be used to create m imputed datasets for each study arm and combined into m analysis datasets with complete data. The choice of m will be determined by the fraction of missing information in the variables to be imputed. [11] MI performed separately within each study arm maintains the structure of the missing data patterns and the relationship between covariates specific to each database and ensures that no outcome information is used in PS matching. [12] Each imputation model will include all covariates listed in Table 4 of Section 6.2 along with the dependent variables and continuous scores for each study outcome as specified in Section 3.0. Dichotomous endpoints will be derived based on continuous scores within each imputed dataset. Analyses will proceed as described in Sections 6.3 and 6.4 using each of the imputed datasets. Finally, treatment effect estimates will be averaged using Rubin's rule [13] to obtain a pooled estimate with standard errors.

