5.5 Statistical Bias Reduction

Studies using observational data are prone to multiple biases. These potential biases in this study are addressed as described below.

Selection Bias. To minimize selection bias for identifying an external control arm for a clinical trial, the study was designed using the target trial emulation framework. [14] The external control arm inclusion/exclusion criteria are carefully defined and matched to the PrismRA arm to reduce potential selection bias. All available patients in the external control arm meeting the criteria for selection will be used in the analyses.

The design of the study is aimed to emulate a randomized clinical trial as closely as possible. In a randomized clinical trial, on average, treated and control groups are balanced with respect to pre-treatment characteristics. The analysis of the entire randomized sample will give the unbiased estimate of the causal effect in the entire trial eligible population. Any "selection" of individuals after randomization could lead to covariate imbalance, change in the population for whom the result may apply, and biased treatment effect estimates. PS methods attempt to emulate the process of randomization by using only pre-treatment covariates (blinded to outcomes and other follow-up observations) to control for potential confounding. We propose a PS model building

process that will estimate a PS for each patient in the entire eligible cohort to be used in analyses of all study objectives.

Information bias. Observational studies relying on retrospective data collection are at risk of information bias, as the accurate assessment of exposures, outcomes and key covariates may be challenged by issues such as the timing of clinical assessments, criteria for treatment response, and documentation in the EMR that vary between and within sites. Objective measures of outcomes and other variables at predefined time points will be used where possible. All data for eligible patients will be extracted and data from multiple sources will be deterministically linked to create a more complete capture of the patient journey. For the external control arm, information on confounders will be limited to data as it is documented in the patient's record.

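### Protocol 8.10 leaves open an undefined option to require follow-up CDAI of external controls only; it conflicts with the rest of the plan and should be deleted.

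*Protocol*

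**What the plan says.** Protocol 8.10 first requires a baseline CDAI of each control in the three months before the index date. It then adds: "As needed, we will further require CDAI during the follow-up". The PrismRA text in the same section deals only with contacting patients and tracing vital status. Protocol 8.9 says that the control arm uses data already held and that nothing new is collected.

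No other section contains this option:

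- Protocol 7.4.1, Table 1 row 8, asks for at least one "CDAI measured in the 3-month period prior to the b/tsDMARD initiation", and at least three measurements in the 12 months before initiation.
- Protocol 10.5: "At least one observed CDAI in the 3-month period prior to the index date (b/tsDMARD initiation) will be required". It sets no follow-up condition.
- SAP 5.4 and SAP 6.1.1 (Table 2 row 8) repeat the pre-index requirements and add no follow-up condition.

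On missing outcomes, SAP 5.4 says "It is anticipated that at 24-weeks roughly 45% of the PrismRA arm and 50% of the external control arm will be missing outcome data" and deals with this by multiple imputation within each arm: "All eligible patients meeting inclusion and exclusion criteria and initiating the study treatment will be used to impute missing observations". SAP 6.3 repeats that scope. SAP 5.5 adds: "All available patients in the external control arm meeting the criteria for selection will be used in the analyses". Restriction to complete CDAI appears in SAP 6.3.2 as a sensitivity analysis, with no limitation to one arm.

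**The concern.** The sentence follows directly on the baseline requirement and extends it, so its natural reading is a further condition for including a control. With no new control data collected, it cannot mean that assessments will be scheduled. It can only be met by leaving out controls who have no follow-up CDAI.

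Membership of one arm would then depend on whether an outcome was recorded after the index date. The control response rate would describe patients who went on being measured, while the PrismRA rate would cover all initiators, about 45% of them imputed at Week 24. Controls removed at this step never enter the imputation model, so imputation cannot represent them. Matching on baseline covariates does not undo selection on a later event, except as far as those covariates explain it.

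The study is unblinded and non-randomized, and at least the historical control follow-up already exists. An open option of this kind is what pre-specification is meant to close.

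**Working it through.** **1. The plan's own figure.** Inputs from Protocol 10.1 and SAP 5.1: 600 PrismRA patients with up to 45% attrition, 1,500 controls with up to 50% attrition, response 40% against 30%, Fisher's exact test, two-sided alpha 0.05.

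- Observed PrismRA: 600 × (1 − 0.45) = 330.
- Observed controls: 1,500 × (1 − 0.50) = 750.
- Exact Fisher power for 330 against 750 is 88.4%; the plan states 88%. The figure reproduces and is not in dispute.

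**2. What that figure presupposes.** Protocol 6.2 and SAP 5.2 expect at least 1,500 eligible controls, of whom at least 750 have both baseline and Week 24 CDAI. So up to 1,500 − 750 = 750 controls in the cohort are expected to have no Week 24 score. If a Week 24 CDAI were a condition of entry, one of two things would follow:

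- the cohort would fall to about 750 controls, all observed, with power still 88.4%; or
- 1,500 controls would all be observed and the 50% attrition input would no longer apply (330 against 1,500 gives 93.0%).

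Neither is the design described. The sample-size section and SAP 5.4 both assume that controls without the outcome stay in.

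**3. Size if the option were used.** Let f be the fraction of controls removed, p_kept and p_removed the response rates in the two groups, and d = p_kept − p_removed. The rate over all controls is (1 − f) × p_kept + f × p_removed, so

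shift = p_kept − overall rate = f × d.

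Take f = 0.50, the largest planned Week 24 missingness. The documents give no value for d, so 4, 8 and 12 points are assumed.

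| d (points, assumed) | Crude shift, f = 0.50 | Share of 10-point target |
|---|---|---|
| 4 | 0.50 × 4 = 2 | 20% |
| 8 | 0.50 × 8 = 4 | 40% |
| 12 | 0.50 × 12 = 6 | 60% |

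The sentence names no visit. If a Week 12 CDAI were enough, f could be smaller, and the shift falls in proportion: with f = 0.25 (assumed), the shifts are 0.25 × (4, 8, 12) = 1, 2 and 3 points.

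The sign of d is unknown. If the retained controls respond worse, the comparison is tilted towards PrismRA; if they respond better, against it.

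**The case against.** The strongest reply is that the SAP has already settled the matter. The Protocol refers to the SAP for analysis detail (10.4) and for missing outcomes in particular (10.5). The SAP requires only pre-index CDAI, expects about half the controls to lack the outcome, and imputes them. An analyst following the SAP alone would never apply the sentence. It could even be a loose reference to the complete-case analysis that Protocol 10.5 lists as one possibility. This stands as far as it goes: the risk is contingent, and the documents do not show that a restricted control arm is planned. But the Protocol still states the option without limits, and no text withdraws it.

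Several stronger readings are tempting and are not supported:

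- A reader might infer that the SAP has a general rule that eligibility uses only pre-treatment data, since SAP 5.5 has the phrase "blinded to outcomes and other follow-up observations". That phrase describes the covariates used in propensity methods. Nor does such a rule hold in practice: row 6 of the exclusion tables (Protocol 7.4.2, SAP 6.1.2) removes controls with pregnancy-related codes during the 24-week follow-up.
- The imputation sentence in SAP 5.4 takes eligibility as given. By itself it does not forbid a further criterion. The conflict comes from reading it with the listed criteria and the expected 50% missingness.
- SAP 5.5 warns that selecting individuals after randomization can bias the effect estimate. The warning concerns the randomized trial being emulated, so it supports the point by analogy and is not a prohibition.
- The shifts of 2 to 6 points are not the bias that this sentence would add. Retained controls would still be matched and the outcome model adjusted, which removes differences explained by measured baseline covariates. Differences due to unmeasured causes would also affect imputation under missing at random. What the sentence adds is therefore smaller than the crude shift, by an amount the documents do not allow one to compute.

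**Conclusion.** The point holds as a conflict within the plan that carries a contingent risk. Protocol 8.10 allows controls, and only controls, to be selected on whether a follow-up CDAI exists. This is incompatible with the CDAI criteria in both documents, with the planned control missingness of up to 50% at Week 24, and with keeping and imputing all eligible initiators.

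The range of 2 to 6 points is an upper-case illustration. It rests on three assumptions: that the rule would remove 50% of controls, that the assumed differences in response apply, and that no adjustment is made. The documents do not show that the option will be used or that it would favour PrismRA. The possible effect is still large enough, and the correction cheap enough, that the sentence should go before the control cohort is fixed.

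**What to change.** In Protocol 8.10, delete the sentence and state instead that:

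1. availability of follow-up CDAI is not an eligibility criterion for controls;
2. missing follow-up CDAI is handled as in SAP 5.4 in both arms;
3. the figure of 750 controls with baseline and Week 24 CDAI (Protocol 6.2, SAP 5.2) is a planning expectation and not a selection rule;
4. any restriction to patients with complete CDAI is made only in the SAP 6.3.2 sensitivity analysis and applies to both arms.

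The new text should be limited to CDAI availability. A broader statement that all control eligibility rests on pre-index data would contradict exclusion row 6 in both documents.

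The cost is a change of Protocol wording through the usual amendment route. Sample size, the stated 88% power and the SAP methods stay as they are.

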8.11 Patient Withdrawal/Completion

PrismRA arm:

Patients may withdraw from the study at any time without prejudice to their care. The Investigator and/or the Sponsor may withdraw patients at any time who violate the study protocol or, to protect the subject for safety or administrative reasons at any time. It will be documented whether or not each patient completes the determined follow-up visits. Changes to the study treatment during follow-up as indicated by clinical practice does not constitute a protocol violation or withdrawal.

Early withdrawals will include, but are not limited to, those patients who consent to participate in the clinical study but fail to initiate a b/tsDMARD at Visit 2 within 6 weeks of Visit 1.

External control arm:

As existing data from routine clinical care will be utilized, this point does not apply.

9 Safety Assessments

9.1 Introduction to Safety Assessments

PrismRA arm:

There are no investigational therapies being evaluated per the protocol. For patients in the informed treatment selection arm, Investigators will receive the PrismRA test results and use the results to inform their treatment decision. PrismRA was developed and its performance characteristics determined by Scipher Medicine. The laboratory is certified under CLIA and accredited under CAP. This commercially available test is used for clinical purposes. It should not be regarded as investigational, or for research. The Investigator is expected to follow all aspects of the prescribing information when administering a pharmaceutical therapy in the course of the treatment of patients included in this study.

External control arm:

Data arise from routine clinical practice and are not subject to study-specific safety assessment.

